# 4. AMENDMENTS AND UPDATES

Amendment number	Date	Substantial or administrative amendment	Protocol section(s) changed	Summary of amendment(s)	Reason
N/A					

Do not distribute for purposes outside of specific activities related to development of FDAMAs114 compliant pieces. Content within this protocol is subject to change based on communication planning and input by external review committees.

Pfizer Confidential

Page 11 of 37

#### Apixaban

NON-INTERVENTIONAL STUDY PROTOCOL

# 5. MILESTONES

Milestone	Planned date
Draft Protocol	10/4/2018
Descriptive Analysis	7/1/2019
Multivariate Analysis	10/1/2019
Final Report	1/20/2020

Do not distribute for purposes outside of specific activities related to development of FDAMAs114 compliant pieces. Content within this protocol is subject to change based on communication planning and input by external review committees.

Pfizer Confidential

Page 12 of 37

Apixaban NON-INTERVENTIONAL STUDY PROTOCOL

# 6. RATIONALE AND BACKGROUND

Atrial fibrillation (AF) is characterized by chaotic and irregular electrical activity in the heart's upper chambers and is the most common heart dysrhythmia diagnosed in the United States. AF has become more prevalent in an aging US population, and this trend is expected to increase exponentially in the coming decades.

AF causes a significant financial burden, costing the US health care system approximately \$26 billion dollars annually. Hospitalizations account for most of these costs (52%).

Vitamin K antagonists, such as warfarin, have been the treatment of choice for anticoagulation. To maximize benefits and minimize complications such as bleeding, warfarin therapy must be monitored and adjusted within a narrow therapeutic index of INR results. Moreover, the pharmacokinetic profile of warfarin is complex due to several drug-drug and drug-food interaction complications. It is also difficult to achieve long-term stability among warfarin patients due to fluctuating INR values, which may be caused by diet, seasonal variation, alcohol consumption, or other factors. The need for regular monitoring, risk of hemorrhage, and poor control of INR levels may lead to medication therapy non-adherence.

In fact, due to its limited therapeutic index and possible drug and food interactions, physicians only prescribe warfarin to about 50% of patients for whom it is recommended. Over the last several years direct oral anti-coagulants (DOACs), including apixaban, dabigatran, edoxaban, and rivaroxaban were approved in the US for stroke prevention among NVAF patients. Clinical trials have demonstrated that DOACs reduce the risk of stroke as much or more than warfarin.

AF is often left untreated after diagnosis. Using registry data of cardiology practices in the United States, it was reported that only 55.1% of patients deemed eligible for warfarin were treated with this agent, and among whom, 35% were not treated with any antithrombotic or antiplatelet. Another US study on patients of outpatient physician practices reported that 23% of NVAF patients did not receive any form of thromboprophylaxis. Moreover, although OACs are recommended for patients with AF and high cardio-embolic risk (according to CHA2DS2-VASc scores), <50% of patients aged 80-89 years are treated with OAC. This may be due to short life-expectancy, fear of bleeding, geriatric syndromes, poor general health, and the overall perception that the harm outweighs the benefits. Yet untreated patients had a lower survival rate and higher association with ischemic stroke events compared to OAC treated patients.

Do not distribute for purposes outside of specific activities related to development of FDAMAs114 compliant pieces. Content within this protocol is subject to change based on communication planning and input by external review committees.

Apixaban

NON-INTERVENTIONAL STUDY PROTOCOL

This study will estimate prevalence of newly diagnosed but untreated NVAF patients, add realworld evidence for the predictors of treatment among newly diagnosed NVAF patients. In addition, it will evaluate the risks of major bleeding, stroke/SE, and death by comparing OAC treatment versus no OAC treatment. The comparative health care costs and utilization will also be evaluated.

# 7. Research Question and Objectives

Primary Objective

- 1. Estimate patients ever-treated and never-treated with OACs and the predictors of OAC treatment among elderly Medicare NVAF patients. The following comparative cohorts will be included:
  - Ever-treated versus never-treated with OACs
  - Treated with DOACs versus never-treated with OACs
  - Treated with warfarin versus never-treated with OACs
  - Treated with DOACs versus treated with warfarin

Secondary Objectives

- 1. Analyze high-risk patient subgroups, including CHA2DS2-VASc score and age subgroups, for the primary objective. The same comparative cohorts as the primary objective will be included. The following subgroups will be examined:
  - ♦ CHA2DS2-VASc score subgroups: 2-3, 4-5, and  $\geq 6$
  - Age subgroups: 65-74, 75-79, and  $\geq$ 80 years
- 2. Compare the risk of major bleeding and major bleeding-related costs among elderly patients treated versus untreated with OACs in the Medicare NVAF population. The following comparative cohorts will be included:
  - Treated versus untreated with OACs
  - ✤ Apixaban versus untreated with OACs
  - Dabigatran versus untreated with OACs
  - Rivaroxaban versus untreated with OACs
  - Warfarin versus untreated with OACs
- 3. Compare the risk of stroke/SE and stroke/SE-related costs among elderly patients treated versus untreated with OACs in the Medicare NVAF population. The same

Do not distribute for purposes outside of specific activities related to development of FDAMAs114 compliant pieces. Content within this protocol is subject to change based on communication planning and input by external review committees.

Apixaban NON-INTERVENTIONAL STUDY PROTOCOL

comparative cohorts as secondary objective 2 will be included.

- 4. Compare the risk of death among elderly patients treated versus untreated with OACs in the Medicare NVAF population. The same comparative cohorts as secondary objective 2 will be included.
- 5. Compare the all-cause health care costs among elderly patients treated versus untreated with OACs in the Medicare NVAF population. The same comparative cohorts as secondary objective 2 will be included.

# 8. Research Methods

# 8.1. Study Design

The study will be a longitudinal retrospective cohort analysis using the US fee-for-service (FFS) Medicare database. This database contains data from inpatient departments, outpatient departments, carrier claims, reported drug events, and beneficiaries' enrollment data. The following will be determined and compared between treatment status (treated with apixaban, dabigatran, edoxaban, rivaroxaban, or warfarin and untreated with OAC): outcomes including major bleeding, stroke/SE, and death; and health care costs and resource utilization. The overall study period will be from 01JAN2012-31DEC2016. The study will designate a 12-month baseline period prior to an index identification period (01JAN2013-31DEC2016). The date of first AF diagnosis during the study period will be assigned as the index date.

Figure 1. Study Periods for Primary and High-Risk Subgroup Objectives

(for illustration purposes only, may not be proportional)

Do not distribute for purposes outside of specific activities related to development of FDAMAs114 compliant pieces. Content within this protocol is subject to change based on communication planning and input by external review committees.

#### Apixaban

NON-INTERVENTIONAL STUDY PROTOCOL

[figure not shown]

Figure 2. Study Periods for Untreated Patients in Secondary Clinical and Healthcare Cost Objectives (for illustration purposes only, may not be proportional)

[figure not shown]

Figure 3. Study Periods for Treated Patients in Secondary Clinical and Healthcare Cost Objectives (for illustration purposes only, may not be proportional)

[figure not shown]
Do not distribute for purposes outside of specific activities related to development of FDAMAs114 compliant pieces. Content within this protocol is subject to change based on communication planning and input by external review committees.

Pfizer Confidential

Page 16 of 37

#### Apixaban

NON-INTERVENTIONAL STUDY PROTOCOL

# 8.2. Setting

Ever treated with OAC and never treated with OAC patients will be selected from 01JAN2013-31DEC2016. To ensure access to the patients' complete medical history, they will be required to have continuous health plan enrollment for the 12 months before the first AF diagnosis date/index date (baseline period). Patient data will be assessed from index date until the earliest of death, health plan disenrollment, treatment switch (treated patients), discontinuation (treated patients), or 31DEC2016 (end of study).

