#### Apixaban NON-INTERVENTIONAL STUDY PROTOCOL

- 4. Compare the risk of death among elderly patients treated versus untreated with OACs in the Medicare NVAF population.
- 5. Compare the all-cause health care costs among elderly patients treated versus untreated with OACs in the Medicare NVAF population.

**Study Design:** The study will be a longitudinal retrospective cohort analysis using the US Centers for Medicare & Medicaid Services (CMS) Medicare dataset from 01JAN2012-31DEC2016. The study will designate a 12-month baseline period prior to the identification period (01JAN2013-31DEC2016). This database only includes patients enrolled in fee-for-service (FFS) Medicare; those enrolled in managed-care plans will be excluded. Further, patient eligibility will be based on selection from the database according to the following inclusion and exclusion criteria (sections 2).

**Population:** Elderly patients (aged  $\geq 65$  years) will be required to have  $\geq 1$  inpatient or  $\geq 2$  outpatient medical claims (the 2 outpatient claims are  $\geq 7$  days apart) for AF during the identification period for the primary and secondary objectives. For the primary objective, two mutually-exclusive NVAF patient cohorts will be created: ever-treated with OAC and never-treated with OAC. For the secondary objective assessing clinical and healthcare utilization and costs, treatment status will be a time-varying covariate and ever-treated patients will contribute time-not-on-treatment to untreated effect.

For the primary and secondary objectives, the ever-treated with OAC population cohort will include newly diagnosed NVAF patients who ever initiated oral anticoagulant (OAC) treatment (apixaban, dabigatran, edoxaban, rivaroxaban, and warfarin) during the study period identified from 01JAN2013-31DEC2016. The never-treated with OAC population cohort will include newly diagnosed NVAF patients without any OAC claim from 01JAN2013-31DEC2016.

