#### Apixaban

Table 2. Clinical and Treatment Pattern Outcome Variables					
Variable	Role	Operational Definition			
Stroke/SE	Outcome	Stroke/SE will be identified using hospital claims with a stroke/SE diagnosis code as the first listed ICD-9-CM or ICD-10-CM code. Stroke/SE will be classified into 3 categories: ischemic stroke, hemorrhage stroke, and SE. Time to stroke/SE will be defined as the number of days from index date to the occurrence of the first stroke/SE requiring hospitalization.			
Major bleeding	Outcome	Major bleeding will be identified using hospital claims with a bleeding diagnosis code as the first listed ICD-9-C or ICD-10-CM diagnosis or procedure code.  Time to major bleeding will be defined as the number of days from index date to the occurrence of the first major bleeding event requiring hospitalization. Major bleeding may be further stratified by gastrointestinal and intracranial hemorrhages and other major bleeding.			
Death	Outcome	Death information from the database will be used. Time to death will be defined as the number of days from index date to death.			
Discontinuation (Treated Patients)	Outcome	Treated patients will be considered to have discontinued if there was no additional refill for the index anticoagulant after 30 days of the previous prescription's run-out date.  The discontinuation date will be defined as the run-out date plus 30 days.			
Time to discontinuation (Treated Patients)	Outcome	Time to discontinuation will be defined as the number of days from the OAC prescription index date to the discontinuation date.			
Switch among anticoagulants (Treated Patients)	Outcome	A switch among anticoagulants will be defined as a prescription filled for non-index anticoagulants within 30 days before or after the run-out date.  Time to switch will be defined as the number of days from the OAC prescription index date to the first prescription date of the switch.			
Time-to-switch (Treated Patients)	Outcome	Time to switch will be defined as the number of days from the OAC prescription index date to the switch date.			

Table 2, Clinic	cal and Treatment Patt	ern Outcome Variables
	cal and frequencine i acc	

Do not distribute for purposes outside of specific activities related to development of FDAMAs114 compliant pieces. Content within this protocol is subject to change based on communication planning and input by external review committees.

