# Inverse Probability Weighting (IPW; Secondary Objectives)

Do not distribute for purposes outside of specific activities related to development of FDAMAs114 compliant pieces. Content within this protocol is subject to change based on communication planning and input by external review committees.

Pfizer Confidential

Page 28 of 37

Apixaban NON-INTERVENTIONAL STUDY PROTOCOL

IPW uses propensity scores to obtain estimates of the average treatment and censoring effect. Propensity scores will be calculated using repeated measures logistic models with: 1) ever-treated with OAC and never-treated with OAC cohorts; 2) each DOAC treated and never-treated with OAC cohorts included in the model, using never-treated patients as the reference (i.e. control cohort). Appropriate correlation structure will be chosen based on the data and clinical rationale.

The propensity score is defined as the probability of a patient receiving OAC/DOAC treatment or being censored conditional on both time-dependent covariates (e.g., comorbidities) and time-independent baseline covariates (age, gender, race, and baseline value for each of the time-dependent variables). The list of variables included in the logistic model will be based on clinical rationale. The propensity score acts as a balancing score among the cohorts.

After calculating the propensity score, the distribution of the propensity scores will be reviewed.

Each patient's weight is equal to the inverse of the probability of their treatment option and censoring (weight=1/propensity score). The numerator of the weight is the propensity score that a patient is on observed treatment/censored in a time period conditional on the baseline covariates. Denominator of the weight is the same propensity score conditional on time-dependent (factors such as CHA2DS2-VASc score, history of bleeding, etc.) and time-independent confounders. If an ever-treated patient has a very low propensity score, a very large weight can be created. Large weights can increase the variability of estimated treatment effect. In order to address this, the weights will be stabilized. Stabilized weights for treatment and censoring will be calculated for each time period of a patient. This reduces the variability of the weights.

$$SW = \prod_{k=0}^{t} \frac{f[A(k) | \overline{A}(k-1), V]}{f[A(k) | \overline{A}(k-1), \overline{L}(k)]}$$

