# Time-Varying Cox Regression Models (Secondary Clinical Objectives)

Time-varying Cox models will be used to compare the time to stroke/SE, major bleeding, and death between: 1) treated vs untreated; 2) each OAC vs untreated after inverse probability treatment weighting. Treatment will be used as a time varying covariate, in order to account for the untreated period of an ever-treated patient. Weights generated using IPW will be incorporated.

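### Ending follow-up at a switch between OACs discards valid treated time in the pooled treated-versus-untreated contrast

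*Protocol*

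**What the plan says.** - **End of follow-up (Section 8.2).** Besides death, disenrollment and the end of the study on 31DEC2016, the events that end follow-up are "treatment switch (treated patients), discontinuation (treated patients"), whichever comes first. The rule stands ahead of the objective-specific criteria and makes no exception by contrast.
- **Switch (Section 8.3, Table 2).** "A switch among anticoagulants will be defined as a prescription filled for non-index anticoagulants within 30 days before or after the run-out date".
- **Discontinuation (Table 2).** It occurs when there is "no additional refill for the index anticoagulant after 30 days" past run-out of the previous supply, and is dated at run-out plus 30 days.
- **Contrasts (Section 7).** Secondary objective 2 lists "treated versus untreated with OACs" beside apixaban, dabigatran, rivaroxaban and warfarin, each against untreated. Objectives 3 to 5 use the same set.
- **Exposure in the model (Section 8.7).** "Treatment will be used as a time varying covariate, in order to account for the untreated period of an ever-treated patient". The abstract adds that "ever-treated patients will contribute time-not-on-treatment to untreated effect".
- **Weights (Section 8.7).** "Stabilized weights for treatment and censoring will be calculated for each time period of a patient". CHA2DS2-VASc and bleeding history are named as time-dependent factors.
- **Sensitivity analyses (Section 8.8).** None of those listed removes censoring at a switch.

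**The concern.** In the pooled contrast, being treated means being on any OAC. A patient who moves from warfarin to a DOAC without a gap has not changed exposure, yet follow-up ends on that date. The rule treats a change of drug as if it were the end of treatment.

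Two things follow. Treated person-time that belongs to the contrast is dropped, together with any events and costs in it. The loss falls on treated patients only, since untreated patients have no drug to switch from. In addition, if the reasons for switching are related to prognosis, the dropped time is a selected part of treated time, and the contrast acquires informative censoring that its own definition of exposure does not require.

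The first consequence follows directly from the text. The second is a possibility: the protocol does not say why patients switch.

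**Working it through.** **1. The definitions applied to the two kinds of contrast**

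| Patient | Drug-specific contrast | Pooled any-OAC contrast |
|---|---|---|
| Fills another OAC within 30 days of run-out (a switch) | No longer on the drug studied; censoring fits | Still treated; Section 8.2 ends follow-up anyway |
| Stops every OAC | Off the drug | Off treatment; the time lost is untreated, not treated |

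The mismatch is in the first row, right-hand column.

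**2. What the index-drug wording for discontinuation adds**

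Illustration: a 90-day supply of the index drug is filled, and another OAC is filled on day 20. That is 90 − 20 = 70 days before run-out, outside the 30-day window, so this fill is not a switch. Without an index-drug refill, discontinuation is dated at day 90 + 30 = 120 while the patient is on another OAC. If a later fill of the second drug falls between days 60 and 120, it counts as a switch instead. Follow-up ends either way. A patient whose second OAC starts more than 30 days after run-out is off treatment under any 30-day gap rule. So this wording adds only patients who change drug more than 30 days before run-out, and most of the issue is the switch rule.

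**3. Which outcomes are exposed**

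Table 2 defines stroke/SE and major bleeding as time to first event, and Table 3 limits the related costs to the first hospitalization.

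- A major bleed that prompts a switch has already been counted as the bleeding outcome. The same holds for a hospitalized stroke and the stroke/SE outcome.
- A bleed that prompts a switch does end follow-up for stroke/SE, and a stroke that prompts a switch ends follow-up for bleeding.
- Any switch ends follow-up for death and for all-cause costs.

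**4. How much treated time could be lost**

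The protocol gives no switch rate or timing, so there is no figure of its own to reproduce. Both calculations below rest on assumptions.

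*Simple form.* Share lost = proportion switching × share of OAC time after the switch, taking switchers and non-switchers to have the same average OAC time.

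- 0.10 × 0.5 = 5%
- 0.20 × 0.5 = 10%

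*Wider form.* Assume administrative follow-up uniform on 0 to 4 years, a constant hazard d of stopping all OACs and a constant hazard s of switching. Mean treated time with total hazard h is

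M(h) = ∫₀⁴ e^(−ht)(1 − t/4) dt = 1/h − (1 − e^(−4h))/(4h²)

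and the share lost is 1 − M(d + s)/M(d). With d = 0.20 and s = 0.10, M(0.20) = 1.558, M(0.30) = 1.392, and 1 − 1.392/1.558 = 10.7%.

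| d per year | s = 0.03 | s = 0.05 | s = 0.10 | s = 0.20 |
|---|---|---|---|---|
| 0.20 | 3.4% | 5.6% | 10.7% | 19.6% |
| 0.50 | 2.8% | 4.6% | 8.8% | 16.4% |
| 0.77 | 2.4% | 3.9% | 7.5% | 14.0% |

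The range is 2.4% to 19.6%, and the simple 5% to 10% lies inside it. The highest d equals −ln(1 − 0.537), the loss figure in Tables 4 and 5 read as annual. It serves only as a high bound for stopping and says nothing about switching. The share of events lost equals the share of time lost only if the event hazard is the same before and after a switch.

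**The case against.** The strongest reply is that censoring at departure from the first regimen is a recognised on-treatment choice. One rule for all five contrasts keeps the pooled result aligned with the drug-specific ones, and the secondary objectives are optional under Section 8.7. The weights also cover censoring in each period, and their named factors include bleeding history and CHA2DS2-VASc, which contains prior stroke. Section 8.10 describes the 100% Medicare database, so losing some person-time is unlikely to decide whether there is enough precision.

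Much of this stands, and it limits the point to fit between rule and contrast, not power. It does not answer that point. The weights act only through measured covariates: Table 1 says INR is unavailable, and Section 8.10 concedes residual confounding. They model a loss that the pooled contrast need not incur. Alignment with the drug-specific contrasts is a convenience, obtained by counting still-treated patients as ended.

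Four stronger readings are tempting but unsupported:

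- **That switches caused by a stroke or bleed bias those same outcomes.** First-event definitions rule this out.
- **That the 53.7% in Tables 4 and 5 shows the problem is large.** It is a planning value for loss to follow-up and does not isolate switching.
- **That the rule biases the comparison in a known direction.** The protocol gives neither the triggers for switching nor the risk after it.
- **That Section 8.2 contradicts the time-varying model.** Time between AF diagnosis and OAC start already supplies untreated time for ever-treated patients.

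Figure 3, on the study periods of treated patients, was not visible for this review and should be checked for an exception.

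**Conclusion.** The point holds as a mismatch between one contrast and the censoring rule applied to it. For the pooled any-OAC comparison, the protocol ends follow-up of patients who remain treated, and no listed sensitivity analysis reverses this. The consequences matter mainly for death, all-cause costs and the cross-outcome cases.

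The size is conditional. It is 5% to 10% of any-OAC treated person-time if 10% to 20% of initiators switch halfway through, and about 2% to 20% over the wider assumed hazards. The possible bias cannot be sized or signed from the protocol, and the planned weights may remove part of it. The rule is coherent for the drug-specific contrasts. The change is worth making before analysis because it is cheap and makes the pooled result match its description, not because a serious bias has been shown.

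**What to change.** In Section 8.2 and Table 2, for the pooled contrast only:

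- define the analytic exposure as any OAC;
- do not censor at a switch between OACs;
- end treated time when no OAC of any kind is refilled within the protocol's existing 30-day gap.

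Keep the index-drug switch and discontinuation rule for the drug-specific contrasts. The treatment and censoring weights for the pooled contrast should then be built on the any-OAC exposure, so that a switch is no longer a censoring event in that weight model.

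The cost is a short addition to the text and one more exposure variable derived from claims already held. The downside is two exposure definitions to program and report, and a pooled contrast that no longer shares its censoring rule with the drug-specific ones. The report should say so wherever the two kinds of result appear together.
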